Appendix 4. Programming Specification

1) AGE calculated as follows:

FTC/RPV/TAF

- a) AGE (years) at each baseline for HIV and HCV study drug is calculated from the number of days between the date of birth (DOB) and first dose date of HIV or HCV study drug,
- b) Use the SAS INTCK function to determine the number of "1st-of-month days" (eg, January 1st, February 1st, March 1st) between DOB and Day 1 (inclusive),
- c) Divide the result in (b) by 12,
- d) AGE = the integer of the result in (c),
- e) If the DOB and the first dose date have the month in common and the birthday is later in the month than the date of first dose, subtract one from the AGE result above.

For subjects randomized and never dosed with any study drug, age at baseline for HIV drug will be calculated from the date of randomization and age at baseline for HCV drug will be set to missing.

- 2) All screened subjects refer to all subjects who are screened (ie, with nonmissing screening date) and have a screening number. For summaries, the same subject is counted only once. DOB and other demographic information such as sex, race, ethnicity, country, and initials will be used to identify unique screened subjects.
- 3) Screen failure subjects are the subjects who answered "No" for any inclusion criteria or "Yes" for any exclusion criteria regardless of which version of protocol the subject was consent to.
- 4) Subjects in All Randomized analysis set are defined as subjects randomized into the study. IXRSRAND is the source to determine whether the subject is randomized (ie, subject with nonmissing RGMNDTN in the IXRSRAND dataset) and confirmed by the eCRF ENROLL dataset (ie, ENROLLYN = "Yes" in ENROLL dataset).
- 5) In disposition table, the reasons for premature discontinuation are displayed in the order as they appear on the eCRF.
- 6) Body mass index (BMI)

Calculated from height in meters (eg, height in cm/100) and weight in kilograms as:

$$BMI = (weight [kg]) / (height [meters]^2)$$

Baseline height and weight will be used for this calculation.

- 7) SAS codes for treatment comparison for demographics and baseline characteristics tables.
 - a) CMH test for nominal variable (Y), p-value from general association test should be used for nominal variable:

```
proc freq order=adsl;
   tables trtgrp * Y /cmh /*general association test*/
run:
```

b) CMH test for ordinal variable (Y), p-value from row mean score test should be used for ordinal variable:

```
proc freq order=adsl;
   tables trtgrp * Y / cmh2 ; /*row mean score test*/
run;
```

c) Wilcoxon rank sum test for continuous variable (Y), p-value from normal approximation two-sided test should be used for continuous variable:

```
proc npar1way wilcoxon data=adsl;
  class trtgrp;
  var Y;
run;
```

8) Please note, "Not Permitted" or missing categories will be excluded for p value generation for categorical data analysis (eg, CMH test or Fisher exact test). Except for Mode of infection (HIV Risk Factors), where "Unknown" will be included for percentage calculation, since a subject may fit more than 1 HIV risk factors, therefore percentage may add to more than 100% and no p-value will be generated.

Subject with Race or Ethnicity = "Not Permitted" will also be excluded to define Race subgroup (ie, black vs. nonblack) or Ethnicity subgroup (ie, Hispanic or nonhispanic) for efficacy subgroup analysis.

9) SAS codes for treatment comparison using Fisher's exact test.

```
proc freq order=adsl;
   tables trtgrp * Y /fisher riskdiff;
run;
```

10) HIV Tagman Calculations

If a HIV-1 RNA test value is reported as "< 20 cp/mL HIV-1 RNA Detected" or "No HIV-1 RNA detected", a numeric value of 19 will be used for summary purpose. "No HIV-1 RNA detected" will be treated as < 20 cp/mL.

11) For table: Number and Percentage of Subjects with HIV-1 RNA < 50 copies/mL by Visit (Missing=Failure):

The denominator for percentages is based on the number of subjects in the full analysis set, excluding ongoing subjects who have missing HIV-1 RNA at a visit and have not reached the upper limit of the analysis window for the corresponding visit.

"Ongoing subjects" refers to subjects who did not discontinued from the study, use the lab data transfer date as the cutoff date.

"Have not reached the upper limit of the analysis window for the corresponding visit" refers to: Cutoff date –first dose date+1< upper limit of the analysis window for a visit.

12) Toxicity Grades:

- a) With regards to Triglycerides, LDL, and Hypercholesterolemia, if the fasting status is not 'Y', in other words it is blank, 'N', or 'U' (for unknown), the lab result value would not be graded since nonfasting values are not interpretable.
- b) For toxicity grade summary, we will include all postbaseline graded results up to 30 days after last dose of study drug, not just those at summarized visits.

b) Fisher's exact test for categorical efficacy response (eg, HIV-1 RNA < 50 copies/mL in US FDA-defined snapshot algorithm), where *trtgrp* is the treatment, and *response* is the categorical efficacy response. P-value from 2-sided Fisher's exact test should be used to test superiority.

```
proc freq data=adeff;
   tables trtgrp*response/fisher; /*p value from Fisher's exact test*/
run:
```

c) ANOVA model for continuous efficacy variable (eg, CD4):

The differences in changes from baseline in CD4 cell count between treatment groups and the associated 95% CI will be constructed using ANOVA, including the prior treatment regimen as fixed effects in the model.

SAS code is as follows:

```
proc glm data=adeffi;
  class trtgrp;
  model CD4 = trtgrp;
  lsmeans trtgrp /alpha=0.05 cl pdiff;
run;
```

Similar code will be used for the analysis of CD4 %.

d) Subgroup analyses

For the subgroups of age, race, sex, region and study drug adherence, p-value from 2-sided Exact method should be used to test superiority. The proportion difference between two treatment groups and 95% CIs are calculated based on an unconditional exact method using 2 inverted 1-sided tests, similarly to that for the primary efficacy endpoint.

14) Treatment-emergent AE (TEAE)

Events with Missing Onset Day and/or Month

The event is treatment emergent in a safety period, if the following 3 criteria are met:

- a) The month and year (or year) of onset date is the same as or after the month and year (or year) of the start date of the safety period, and
- b) The month and year (or year) of the onset date is the same as or before the month and year (or year) of safety cutoff date of the safety period, and
- c) AE end date is as follows:
 - i) The (complete) AE end date is on or after the safety period start date, or
 - ii) The month and year (or year) of end date is the same or after the month and year (or year) of the safety period start date, or
 - iii) AE end date is completely missing.

Events with Completely Missing Onset Date

An AE with a completely missing onset date is defined as TEAE for a safety period if AE end date meets any of the criteria specified in 3) above.

15) Renal related laboratory evaluation

Urine Protein Correction

a) The calibrator material used in the quantitative assay for the measurement of urine protein (UP) was changed globally in Covance on May 27, 2016. All samples reported prior to May 27, 2016 (ie, *RPTDTM* < 'May 27, 2016') were tested by the calibrator material manufactured by Roche Diagnostics, while the samples reported on or after May 27, 2016 were tested by the calibrator material manufactured by Quantimetrix. Covance had 3 regional lab centers to run the samples. Each regional lab center conducted its own alternate (quantitative) method comparison, all of these comparison demonstrate that calibrator materials manufactured by the Roche and Quantimetrix yield comparable results as noted in the table below:

Regional Lab Center	Accession Numbers ^a	Regular Regression for UP Correction ^b	Correlation Coef.	Bias
Indianapolis Auto Chemistry	Start with 65	Y = 1.028 X - 3.70	0.9982	-2.34 (-4.91%)
Geneva Auto Chemistry	Start with 62 or 63	Y = 0.981 X - 1.44	0.9993	-2.42 (-4.74%)
Singapore Auto Chemistry	Start with 64 or 66	Y = 0.980 X - 1.62	0.9996	-2.73 (-5.08%)
BML in China	Start with 67 or 68	NA	NA	NA

a Accession numbers specified which regional lab center tested the sample . For example, samples with accession number started with 65 were tested in Indianapolis Auto Chemistry Center.

b X and Y are the UP results using calibrator materials manufactured by Roche Diagnostics and Quantimetrix, respectively.

b) In order to combine UP results from 2 different assay methods for summary/comparison purpose, we will convert the UP results analyzed using the calibrator from Roche (ie, results reported prior to May 27, 2016) to Quantimetrix results by using the regression equation listed in above table.

Original UP based on Reported Date	Original UP Categories	Accession Number	AVALC of Corrected UP ('UP' stands for Original UP)			
UP reported on/after May 27, 2016	_ALL_	_ALL_	AVALC of UP			
	UP < 4.0	_ALL_	'< 4.0'			
UP reported before May 27, 2016	UP ≥ 4.0	Start with 65	$1.028 \times \text{UP} - 3.70$; if $1.028 \times \text{UP} - 3.70 \ge 4.0$ '< 4.0 '; if $1.028 \times \text{UP} - 3.70 < 4.0$			
		Start with 62 or 63	$0.981 \times UP - 1.44$; if $0.981 \times UP - 1.44 \ge 4.0$ '< 4.0 '; if $0.981 \times UP - 1.44 < 4.0$			
		Start with 64 or 66	$0.980 \times \text{UP} - 1.62$; if $0.980 \times \text{UP} - 1.62 \ge 4.0$ '< 4.0 '; if $0.980 \times \text{UP} - 1.62 < 4.0$			

c) The corrected UP results will be used for the following analysis and referred as "UP" in following text. If AVALC of the corrected UP is "< 4.0", the AVAL of the corrected UP will be imputed as 3.9 mg/dL.

Unit conversion for renal safety tests derived from related tests with conventional units

- a) Urine RBP (ug/L) to creatinine (mg/dL) ratio: $1 (ug/L) / (mg/dL) = 100 \times ug/g$
- b) Urine Beta-2-microglobulin (mg/L) to creatinine (mg/dL) ratio: $1 \text{ (mg/L)} / \text{ (mg/dL)} = 10^5 \text{ ug/g}$
- c) Urine Protein (mg/dL) to creatinine (mg/dL) ratio: 1 (mg/dL) / (mg/dL) = 1000 x mg/g
- d) Urine Albumin (mg/dL) to creatinine (mg/dL) ratio: 1 (mg/dL) / (mg/dL) = 1000 x mg/g

Calculation of ratios:

To calculate laboratory ratios (eg, urine RBP to creatinine ratio), the lab value of each test in the ratio needs to be from the same accession number; if any test value used for the ratio calculation from the same accession number is missing, then the ratio is not calculable (ie, missing). For urine creatinine, a value of "< 1" is handled as a missing value in the calculation of related ratios. For urine protein, a value of "< 4.0" is handled as a missing value in the calculation of UPCR.

Combined category of UP and UPCR

- a) First merge UP and UPCR based on the subject identifier and accession number.
- b) At each visit, based on UP to select which pair of records should be used for the analysis. That is, once a UP record is selected for that visit, the UPCR with the same accession number (if calculated) will be selected. Please note, UPCR is missing when UP < 4.0 mg/dL.
- c) Subject will be classified as "UPCR ≤ 200 mg/g" if UP < 4.0 mg/dL or UPCR ≤ 200 mg/g; Subject will be classified as "UPCR > 200 mg/g" if UPCR > 200 mg/g; Otherwise, subject will be classified as "Missing".
- 16) Concomitant nonstudy-drug ARV medications (ie, ARV medications other than study drug that are taken while receiving study drug) will be flagged in "Nonstudy-Drug Antiviral Medication" listing. The logic to define concomitant nonstudy-drug ARV is similar to concomitant non-ARV Medications (see details in Section 7.4.2).
- 17) Age for laboratory test reference range will be based on the age at the sample collection date.

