3.3. Strata and Covariates

Randomization was stratified by race (black or non-black) to provide balance across treatment groups.

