5.2. Baseline Disease Characteristics

The following study baseline disease characteristics will be summarized for Safety Analysis Set by treatment group and overall, using data collected prior to or on **Study Day 1**:

- HIV-1 RNA categories (copies/mL): (a) < 50, (b) ≥ 50
- CD4+ cell count (/μL)
- CD4+ cell count categories (/ μ L): (a) < 50, (b) \geq 50 to < 200, (c) \geq 200 to < 350, (d) \geq 350 to < 500, and (e) \geq 500
- CD4 percentage (%)
- HIV risk factors (mode of infection)
- HIV disease status
- eGFR_{CG} at Study Baseline (mL/min)
- Duration of prior ARV treatment (years)
- Log₁₀ HCV RNA at Study Baseline (log₁₀ IU/mL)
- HCV RNA Category at Study Baseline: (a) < 800,000 IU/mL; (b) $\ge 800,000 \text{ IU/mL}$

In summary of disease characteristics at the study baseline, for categorical data, the Cochran-Mantel-Haenszel (CMH) test (general association statistic for nominal data, and row means scores differ statistic for ordinal data) will be used to compare the 2 treatment groups. For continuous data, the 2-sided Wilcoxon rank sum test will be used to compare the 2 treatment groups.

The following Part 2 baseline disease characteristics will be summarized for Part 2 Safety Analysis Set by treatment group and total within each HCV genotype (1a, 1b, and other if applicable) and overall, using data collected prior to or on **Part 2 Day 1**:

- Log₁₀ HCV RNA at Part 2 Day 1 (log₁₀ IU/mL)
- HCV RNA Category at Part 2 Day 1: (a) < 800,000 IU/mL; (b) $\ge 800,000 \text{ IU/mL}$
- IL28B
- Cirrhosis
- Cirrhosis determination method
- ALT at Part 2 Baseline
- ALT category at Part 2 Baseline: (a) $\leq 1.5 \times \text{ULN}$; (b) $> 1.5 \times \text{ULN}$
- Prior HCV treatment experience: (a) treatment-naïve; (b) treatment-experienced
- eGFR_{CG} at Part 2 Baseline (mL/min)

In summary of disease characteristics at Part 2 baseline, no between treatment p-value will be calculated.

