6.3.2.7. Analysis of CD4+ Cell Count and CD4 %

Both CD4 cell count and CD4 % will be summarized using observed, on-HIV-treatment data (ie, data collected up to 1 day after permanent discontinuation of HIV study drug or all available data for subjects who are still on HIV study drug) for subjects in the HIV FAS.

The change from baseline in CD4+ cell count will be summarized by visit for each treatment group and over all using descriptive statistics. The differences in changes from baseline 24 weeks after start of HIV study drug in CD4+ cell count between the 2 treatment groups and the associated 95% CI will be constructed using ANOVA models, including treatment group and race as fixed effects.

In addition, the change from baseline in CD4+ cell counts with missing values imputed using the last observation carried forward (LOCF) method will be summarized at each visit based on the FAS. The algorithm for LOCF as follows:

- If a value is missing in an analysis visit window, the missing value will be replaced with the last on-HIV-treatment value (ie, data collected up to 1 day after the last dose date of HIV study drug) observed before the analysis visit window that has the missing value.
- Baseline values will be carried forward to impute the postbaseline value at a specific visit, if there is no nonmissing postbaseline observation collected prior to that visit.

CD4% will be analyzed the same as CD4+ cell count, except that the by-visit summary using LOCF method is not planned for CD4%.

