7.4. Prior and Concomitant Medications

7.4.1. Nonstudy Drug Antiretroviral Medications

Any nonstudy drug ARV medications used prior to, during, or after the study (if collected) will be coded using the GSI-modified World Health Organization (WHO) Drug Dictionary. The WHO preferred name and drug code will be attached to the clinical database. All nonstudy drug ARV medications will be listed. No inferential statistics will be provided.

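### The SAP gives three different models for the between-arm CD4 comparison: treatment plus race, prior treatment regimen, and (in the code) treatment alone

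*SAP*

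**What the plan says.** SAP Section 6.3.2.7 covers CD4+ cell count and CD4%, both tertiary endpoints. Besides descriptive summaries by visit, it plans one between-arm comparison: the difference in change from baseline 24 weeks after the start of HIV study drug, with a 95% CI, "constructed using ANOVA models, including treatment group and race as fixed effects".

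SAP Appendix 4, item 13c, is the programming instruction for continuous efficacy variables, with CD4 as its example. Its text also concerns "The differences in changes from baseline in CD4 cell count between treatment groups", but fits the ANOVA "including the prior treatment regimen as fixed effects in the model". Race is not mentioned. The SAS code that follows declares treatment as the only class variable and has the statement "model CD4 = trtgrp". The item closes with "Similar code will be used for the analysis of CD4" %.

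On covariates more generally, SAP Section 3.3 says only this: "Randomization was stratified by race (black or non-black) to provide balance across treatment groups". Section 5.2 summarises the duration of prior ARV treatment in years, not its composition. Section 7.4.1 codes non-study ARV drugs with a drug dictionary and then states: "All nonstudy drug ARV medications will be listed. No inferential statistics will be provided".

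Protocol Section 8.4.2 plans descriptive CD4 summaries only, at Week 8 and Post-HCV Treatment Week 12.

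**The concern.** One pre-specified estimate should come from one model. Here the body text, the appendix text and the appendix code each name a different one, and neither document states an order of precedence. The protocol cannot settle it because it has no CD4 model.

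A programmer who copies the supplied code would leave out the only randomisation stratum, which Section 6.3.2.7 requires. One who follows the appendix text would first have to decide what prior regimen means and how to group it, a decision that in an open-label trial could be made with outcome data in view. The code also names its response CD4 although both texts analyse change from baseline. If that variable held absolute counts, the wrong quantity would be modelled.

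**Working it through.** **Setting the three specifications side by side**

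| Source | Response | Fixed effects | Residual df if all 120 subjects have data |
|---|---|---|---|
| Section 6.3.2.7 | change from baseline at Week 24 | treatment, race (2 levels) | 120 - 3 = 117 |
| Item 13c, text | change from baseline | prior regimen (treatment implied) | 118 - (k - 1), with k undefined |
| Item 13c, code | variable named CD4 | treatment | 120 - 2 = 118 |

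Item 13c does not name Week 24. The 24-week comparison in Section 6.3.2.7 is, however, the only between-arm CD4 ANOVA in the SAP, so it is the analysis that item 13c implements.

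The documents state no figure that depends on this model. They also give no CD4 standard deviation, race effect or regimen effect. The sizes below are therefore illustrations on stated assumptions, in units of the residual SD.

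**Treatment plus race against treatment alone**

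Assume race is balanced between arms. Let *p* be the proportion of black subjects and *d* the race effect in residual SDs. With exact balance the estimated treatment difference is the same in both models. Leaving race out moves its variance into the residual, so approximately

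SE ratio (without / with race) = sqrt(1 + p(1 - p)d²).

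Take *p* = 0.34, the share reported for the HIV/HCV coinfection study ION-4 in Protocol Section 1.3.2, where p(1 - p) = 0.34 × 0.66 = 0.2244:

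- *d* = 0: 1.000
- *d* = 0.5: sqrt(1 + 0.2244 × 0.25) = 1.028
- *d* = 1: sqrt(1 + 0.2244) = 1.107

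At *p* = 0.5 the ratios are 1.000, 1.031 and 1.118. The code version is thus between 0% and about 12% less precise over this range.

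**Treatment plus race against treatment plus prior regimen**

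This was simulated with N = 120, two arms of 60, 4,000 replicates, race balanced by arm, regimen in equal classes but not stratified, and no race effect unless stated. CI ratio is mean CI width, regimen model over race model. Shift is the root-mean-square difference between the two estimates, in SEs.

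| Regimen classes | Between-class SD | Race effect | CI ratio | Shift |
|---|---|---|---|---|
| 3 | 0 | 0 | 1.009 | 0.13 SE |
| 3 | 0.25 | 0 | 0.98 | 0.28 SE |
| 3 | 0.5 | 0 | 0.902 | 0.47 SE |
| 3 | 0.5 | 0.5 | 0.93 | 0.47 SE |
| 8 | 0 | 0 | 1.032 | 0.25 SE |
| 8 | 0.5 | 0 | 0.923 | 0.49 SE |

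Unlike the race comparison, this one moves the point estimate even when regimen has no effect, because an unstratified factor is never exactly balanced. The result also depends on the number of classes, which the SAP does not fix.

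**The case against.** The best case against raising this is that item 13c looks like text carried over from another study. Item 13d lists a region subgroup that Section 3.4.1 does not have, and the example data in item 13a show 189 successes in one arm where about 60 subjects are planned. On that view nobody intended a prior-regimen model. Section 6 is the analysis specification, Section 3.3 names only race, and the body text is the natural one to follow. Carry-over is the likely explanation, and it supports Section 6.3.2.7 as the intended model. It does not remove the conflict: the only executable instruction still contradicts the body, and nothing tells the programmer to disregard it.

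It is also fair that the CD4 name in the code may be a placeholder, since other items use generic names and the sentence above the code says change from baseline. That part is minor and deserves only a clarifying edit.

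A prior-regimen factor could be built. Prior ARV drugs are coded under Section 7.4.1, and Protocol Table 4-1 groups permitted agents by class. What stands is that the SAP does not say which grouping to use, so any version would involve an unplanned choice.

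Finally, the sizes depend on assumed effects, and the stakes are low. CD4 change is tertiary, is reported as an estimate with a CI and no stated hypothesis, and goes beyond the protocol's descriptive plan. All of that stands and limits the weight of the point.

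**Conclusion.** The inconsistency is certain from the text; its consequence is modest. Following the code omits the stratum required by Section 6.3.2.7. With exact race balance among subjects who have Week 24 data, that leaves the estimate unchanged and costs 0% to about 12% in standard error for race effects up to 1 residual SD. If that balance is lost through missing data, the estimate can move too. Following the appendix text replaces a stratum with an undefined factor: in the cases examined, the CI ranges from about 3% wider to about 10% narrower and the estimate shifts by 0.13 to 0.49 SE. These figures rest on assumed race and regimen effects and complete data on 120 subjects.

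No primary or secondary efficacy result depends on this model, and SVR12 is unaffected. It should be corrected before the analysis is programmed, because the three versions can report different intervals and the remedy is almost free.

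**What to change.** Align Appendix 4 item 13c with Section 6.3.2.7:

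- Delete the prior-regimen phrase and name treatment group and race (black, non-black) as the fixed effects.
- Name the response as change from baseline at Week 24.
- Replace the code with, for example, `class trtgrp race; model chg = trtgrp race; lsmeans trtgrp / alpha=0.05 cl pdiff;`.
- State that CD4% uses the same model.
- State whether race is the stratum used at randomisation or the collected value, and how a race recorded as not permitted is handled. Item 8 of Appendix 4 covers that only for categorical p-values and subgroups.

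The cost is SAP wording and one or two lines of code, on data already collected.

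Separately, and as an efficiency option rather than a correction, baseline CD4 (baseline CD4% for CD4%) could be added as a covariate in both places. With equal variances at baseline and Week 24 and correlation *r* between them, the SE ratio against ANOVA of change is sqrt((1 - r²) / (2(1 - r))): 0.866 at *r* = 0.5 and 0.949 at *r* = 0.8, a gain of about 13% to 5%. The correction above does not depend on it.
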